### **11.5.1 Reproductive risks:**

Patients should not become pregnant or father a baby while on this study because the drugs in this study can affect an unborn baby. A woman should NOT CONCEIVE A BABY while she or her partner is receiving lenalidomide. A man should NOT DONATE SPERM OR IMPREGNATE HIS PARTNER while he is on lenalidomide.

Women should not breastfeed a baby while on this study. It is important that the patient understand that they will need to use birth control while on this study. A list of acceptable forms of birth control methods to use and how long to use them is listed below. Pregnancy testing will be required as per Table 7.

### 11.5.2 Pregnancy Risk – Females:

If a patient is a female of childbearing potential\*, she will be required to have two negative pregnancy tests: the first test within 10-14 days before lenalidomide is prescribed and the second test within 24 hours before lenalidomide is prescribed.

\* For the purposes of this study, a female of childbearing potential is a sexually mature female who: 1) has not undergone a hysterectomy (the surgical removal of the uterus) or bilateral oophorectomy (the surgical removal of both ovaries) or 2) has not been naturally postmenopausal for at least 24 consecutive months (i.e., has had menses at any time during the preceding 24 consecutive months).

The female patient will be required to use **TWO** reliable forms of birth control, one highly effective method and one additional effective method at the same time or practice complete abstinence from heterosexual intercourse during the following time periods related to this study: 1) for at least 28 days before starting lenalidomide; 2) throughout lenalidomide therapy, including interruptions in therapy; and 3) for at least 28 days after discontinuation of lenalidomide. The following are the acceptable birth control methods:

Highly Effective Method	Additional Effective Methods
Intrauterine device (IUD)	Latex condom
Hormonal (birth control pills, injections, implants)	Diaphragm
Tubal ligation	Cervical Cap
Partner's vasectomy	

A female patient must not breastfeed a baby while participating in this study and for at least 28 days after the discontinuation of lenalidomide.

Females of childbearing potential with regular or no menstrual cycles must agree to have pregnancy tests weekly for the first 28 days and then every 28 days while taking lenalidomide, at the time lenalidomide is discontinued, and at day 28 following discontinuation of lenalidomide. If menstrual cycles are irregular, the pregnancy testing must occur weekly for the first 28 days and then every 14 days while taking lenalidomide, at discontinuation of lenalidomide, and at days 14 and 28 following discontinuation of lenalidomide.

If the patient has any reason to suspect that they are pregnant, the patient must IMMEDIATELY stop taking lenalidomide and contact the physician investigator.

### **11.5.3 All Patients:**

Patients must **NEVER** share lenalidomide with someone else. The patient must receive counseling and complete phone surveys as required by the **Revlimid REMS®** program.

The patient should be instructed to swallow lenalidomide capsules whole with water at the same time each day. They should not break, chew or open the capsules.

If the patient misses a dose of lenalidomide, they should take it as soon as they remember on the same day.

If they miss taking the dose for the entire day, they should take the regular dose the next scheduled day (they should NOT take a double regular dose to make up for the missed dose).

If they take more than the prescribed dose of lenalidomide they should seek emergency medical care if needed and contact the study staff immediately.

Females of childbearing potential that might be caring for you should not touch the lenalidomide capsules or bottles unless they are wearing gloves.

Any unused Revlimid® (lenalidomide) should be returned as instructed through the **Revlimid REMS®** program.

## **12.0 CRITERIA FOR THERAPEUTIC RESPONSE/OUTCOME ASSESSMENT**

### **12.1 Multiple Myeloma:**

Responses will be determined according to the IMWG Response Criteria (that have supplanted the older European Group for Blood and Marrow Transplantation (EBMT) criteria) using standard electrophoretic and immunofixation tests of serum and urine for a monoclonal protein (M protein), the serum free light chain assay, and the bone marrow aspirate and biopsy with immunohistochemical staining. [Rajkumar SV, 2011]

For all patients responses will be assessed at the end of each cycle. Patients will have response of the myeloma assessed with serum and urine protein electrophoresis (SPEP/UPEP), serum and urine immunofixation (IF), quantitative immunoglobulins, and serum free light chain assay. A Patients will have a repeat bone marrow biopsy to confirm a biochemical complete response .

#### **12.1.1 Response Criteria**

Responses are as follows for patients with measurable M protein:

- Stringent Complete Response (sCR) = Undetectability of the M protein by immunofixation of serum and urine, normalization of the serum free light chain ratio, and normalization of the bone marrow biopsy, including  $\leq 5\%$  total plasma cells and lack of clonal excess by kappa/lambda staining.
- Complete Response (CR) = Undetectability of the M protein by immunofixation of serum and urine or normalization of the serum free light chain ratio in patients without a detectable serum or urine M-spike at baseline and normalization of the bone marrow biopsy, including  $<5\%$  total plasma cells and lack of clonal excess by kappa/lambda staining.
- Very Good Partial Response (VGPR) = Serum and urine M component detectable by immunofixation only but not by electrophoresis or a reduction of  $\geq 90\%$  in the M-protein concentration component plus a urine M-component  $<100\text{mg}/24\text{ hours..}$
- Partial Response (PR) = 50% or greater reduction of serum M-protein and reduction in 24-hour urinary M-protein by  $>90\%$  or to  $>200\text{mg}/24\text{ hours.}$  If the serum and urine M-protein are not measurable, a decrease of 50% in the difference between involved and uninvolved FLC levels is required in place of M-protein criteria. In addition to the above criteria, if present at baseline,  $>50\%$  reduction in the size of soft tissue plasmacytomas is also required.
- Minimal Response (MR) = A reduction of  $>25\%$  but  $<50\%$  in the M-protein concentration.
- Stable disease (SD) = An increase in the M protein by  $< 25\%$  from baseline or a decrease in the M protein by  $< 25\%$  from baseline.
- Progressive Disease (PD) = Increase of 25% from lowest response value in any of the following: serum M-component (minimal absolute increase of  $0.5\text{g/dl}$ ), urine M-component (absolute increase must be  $200\text{mg}/24\text{h}$ ), and/or only in patients without measurable serum and urine M-protein levels: the difference between involved and uninvolved FLC levels (absolute increase must be  $10\text{mg/dl}$ ) and/or the occurrence of new hypercalcemia, new lytic lesions by skeletal survey, or new soft tissue plasmacytomas.

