- Grade 4 hematologic toxicities (attributed to study drugs) defined as:
  - Grade 4 thrombocytopenia (platelets  $< 25$  K/ $\mu$ L)
  - Grade 4 neutropenia (absolute neutrophil count (ANC)  $< 0.5$ )
- Grade 3 thrombocytopenia or neutropenia that results in a  $> 4$  day delay in any romidepsin dose in cycle 1.
- One week or greater delay in initiating cycle 2 day 1 due to continued drug-related toxicity.

At the time of enrollment the patients will be identified as representing three cohorts based upon disease subtype: 1) B-cell lymphoma 2) multiple myeloma 3) PTCL. Each disease specific cohort will enroll 15 patients. We plan to accrue 38 patients into the phase IIa portion including those treated at the MTD of the phase Ib portion. The assessment of toxicity and efficacy will be performed within the entire cohort evaluable at MTD. A preplanned exploratory analysis of the toxicity and efficacy of the disease specific cohorts will also be performed. Efficacy measures which will be determined include ORR, CBr (for myeloma), TTR, DOR, and EFS. ORR is defined as the percentage of patients achieving a best response of CR/CRu, very good partial response (VGPR--myeloma only), or PR at any disease assessment time point. CBr is defined as CR, VGPR, PR or MR (minimal response) in myeloma patients. TTR is defined as the time or number of cycles between study registration and documentation of first response (CR/Cru, VGPR, or PR). DOR is defined as the time or number of cycles between documentation of first response and progression, change of therapy, death, or date of last contact (if still alive without progression). EFS is defined as the time between study registration and documented progression, change in therapy, or death if no progression was observed.

[figure not shown]

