## **6.0 CRITERIA FOR SUBJECT ELIGIBILITY.**

### **6.1 Subject Inclusion Criteria**

1. Pathology confirmed lymphoma or multiple myeloma.
  - Hodgkin lymphoma is eligible for either phase and will be considered a B-cell lymphoma in the phase IIa study.
  - Phase IIa portion, subjects must have B-cell lymphoma, T-cell lymphoma, or multiple myeloma.
2. Relapse or progression after at least 1 systemic therapy.
3. Measurable disease for phase IIa portion only.

- Lymphoma (includes CTCL patients who are NED in skin): CT or PET/CT by modified Cheson criteria with incorporation of PET.
  - Multiple myeloma: Patient must have measurable disease and therefore must have at least one of the following:
    - i. Serum M-protein  $\geq 0.5\text{gm/dL}$  ( $\geq 5\text{gm/L}$ )
    - ii. Urine M-protein  $\geq 200\text{mg/24hr}$
    - iii. Serum FLC assay: involved FLC  $\geq 10\text{mg/dL}$  ( $\geq 100\text{mg/L}$ ) provided serum FLC ratio is abnormal.
  - CTCL: mSWAT  $>0$ , or absolute Sezary count  $\geq 1000\text{ cells}/\mu\text{L}$ .
4. Age  $\geq 18$  years at the time of signing the informed consent form.
  5. Able to adhere to the study visit schedule and other protocol requirements.
  6. Previous systemic anti-cancer therapy must have been discontinued at least 3 weeks prior to treatment in this study. If there is progression of disease on that therapy and all adverse effects have resolved to Grade 1 or baseline, in which case 2 weeks is acceptable.
  7. Previous radiation, hormonal therapy, and surgery must have been discontinued or completed at least 2 weeks prior to treatment in this study and adverse effects must have resolved. Lymph node or other diagnostic biopsy within 2 weeks is not considered exclusionary.
  8. Short course systemic corticosteroids for disease control, improvement of performance status or non-cancer indication (< 7 days) must have been discontinued at least 7 days prior to study treatment. Stable ongoing corticosteroid use ( $\geq 30$  days) up to an equivalent dose of 15 mg of prednisone is permissible.
  9. ECOG performance status of  $\leq 2$  at study entry (see Appendix A).
10. Laboratory test results within these ranges:
- Absolute neutrophil count  $\geq 1.0/\text{mm}^3$ .
  - Platelet count  $\geq 70\text{ K}/\mu\text{L}$ , if thrombocytopenia is due to bone marrow involvement platelet count must be  $\geq 50\text{ K}/\mu\text{L}$ .

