### **12.1.2 Special Considerations in Assessing Response**

Low-level urinary M proteins may vary from measurement to measurement. For an increase in urinary M protein to be considered progression of disease it must be an absolute increase of at least  $200\text{ mg/day.}$

In quantitative immunoglobulin serum studies, the levels of heavy and light chain are often discrepant for technical reasons. If the discrepancy leads to equivocal response values, the heavy-chain value will be used since the heavy-chain value is usually a more reliable indicator because of its longer half-life and non-renal metabolism.

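### As printed, the absolute urine limb of the myeloma partial-response definition points the wrong way: it accepts urine M-protein that stays above 200 mg/24 h and rejects larger falls

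*Combined protocol and SAP*

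**What the plan says.** Section 12.1.1 lists the myeloma response categories. PR requires "50% or greater reduction of serum M-protein and reduction in 24-hour urinary M-protein by" more than 90%, or, as the alternative, a reduction to a stated level. In the machine-read text (with its markup) that level is ">200\text{mg}/24\text{ hours", that is, above 200 mg per 24 hours.

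Other provisions that bear on this:

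- **VGPR (12.1.1).** The 90% route is a reduction in M-protein "plus a urine M-component" below 100 mg/24 h.
- **MR (12.1.1).** "Minimal Response (MR) = A reduction of" more than 25% but less than 50%. Stable disease is a change of less than 25% in either direction.
- **PD (12.1.1, 12.1.2).** A urine rise counts only if it is at least 200 mg/24 h in absolute terms. Section 12.1.2 adds that "Low-level urinary M proteins may vary from measurement to measurement".
- **Entry (6.1, criterion 3).** For phase IIa, "Patient must have measurable disease and therefore must have at least one of the following": serum M-protein, urine M-protein of at least 200 mg/24 h, or free light chains.
- **Endpoints (4.1).** ORR counts CR, VGPR "or PR at any disease assessment time point". CBr adds MR. "TTR is defined as the time or number of cycles between study registration and documentation of first response", and DOR runs from that first response.
- **Analysis (1.0, 14.0).** The VGPR/PR rate is also reported, and myeloma is pooled with the lymphomas. Results are proportions with confidence intervals and Kaplan-Meier or competing-risks summaries.
- **Timing (12.1).** Myeloma response is assessed at the end of every cycle.

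**The concern.** A response criterion should not be easier to meet when more disease marker remains. With the printed sign, the absolute urine limb is met by urine that stays high and failed by urine that falls low. Some patients with a genuine serum and urine response would then be refused PR, and others with almost no urine response would be credited with it.

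The consequence is confined to secondary myeloma endpoints and the pooled efficacy summary: ORR, CBr, the VGPR/PR rate, TTR and DOR. EFS does not use PR. The primary objective (MTD and toxicity), the DLT rules and the sample size do not use it either.

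**Working it through.** **Inputs.** The PR, VGPR, MR and PD definitions come from 12.1.1 and the entry threshold from 6.1. The myeloma cohort is 8 (14.0) or 15 (4.1 and 9.3). The pooled number is about 44 at the MTD (14.0), 38 (4.1) or up to 51 (9.3). The plan gives no figure of its own to reproduce here.

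**Direction, from the protocol alone.** VGPR, the next better category, requires urine below 100 mg/24 h by its 90% route. PD treats a urine rise as worse. Entry treats urine of 200 mg/24 h or more as measurable disease. In all three, higher urine is worse; only the absolute PR limb runs the other way.

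**The two rules.** Let U0 be baseline and U follow-up urine M-protein in mg/24 h, with U < U0. Assume the serum fall is at least 50% but below the VGPR level.

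- Printed: PR if U < U0/10, or U > 200.
- Sign reversed: PR if U < U0/10, or U < 200.

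**Baseline 1,000.**

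| Follow-up U | Fall | Printed | Reversed |
|---|---|---|---|
| 900 | 10% | PR | not PR |
| 250 | 75% | PR | not PR |
| 150 | 85% | not PR | PR |
| 90 | 91% | PR | PR |

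As urine improves from 250 to 150 to 90, the printed rule gives PR, then not PR, then PR. PR with urine above 200 is not wrong in itself: 5,000 to 400 is a 92% fall and qualifies under both rules.

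**By baseline.**

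- U0 of 200 or less: no reduction can end above 200, so only a fall of more than 90% gives PR.
- U0 above 200 and up to 2,000: the printed rule is non-monotone, failing from U0/10 to 200 and passing on both sides. At 2,000 only U = 200 fails.
- U0 above 2,000: nobody is refused, but any fall at all gives PR.

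With the sign reversed, PR holds when U is below the larger of U0/10 and 200, which is monotone at every baseline.

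| U0 | Refused only as printed | Granted only as printed | Whole-number values of U that disagree |
|---|---|---|---|
| 150 | 15–149 | none | 135 of 150 |
| 300 | 30–199 | 201–299 | 170 + 99 = 269 of 300 |
| 500 | 50–199 | 201–499 | 150 + 299 = 449 of 500 |
| 1,000 | 100–199 | 201–999 | 100 + 799 = 899 of 1,000 |

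These counts show how far the two rules differ. They are not probabilities or patient counts.

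**Effect on ORR and TTR (cycles 1, 2, 3).**

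| U0 and sequence | Printed | Reversed | Effect of printed rule |
|---|---|---|---|
| 1,000: 250, 150, 90 | Y, N, Y | N, Y, Y | first response one cycle early |
| 1,000: 150, 120, 90 | N, N, Y | Y, Y, Y | first response two cycles late |
| 150: 100, 80, 60 | N, N, N | Y, Y, Y | never a responder |
| 1,000: never below 900 | Y | N | false responder |

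In the second row, had urine stopped at 120 (an 88% fall), the patient would never be PR as printed. Because ORR takes PR at any assessment, one reading above 200 is enough to grant it, while a refusal lowers ORR only if no assessment qualifies. With the progression date fixed, DOR moves opposite to TTR: one cycle longer in the first row, two shorter in the second.

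**No fallback category.** A patient refused PR on urine alone has a serum fall of at least 50%, which fits neither MR nor SD on serum change, and so can drop out of CBr as well. This gap exists under either sign; the sign decides who falls into it.

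**Clash with VGPR.** Serum down 92% with urine 500 to 80 meets VGPR (reading its 90% fall as serum). It fails the PR clause, since 80 is an 84% fall and is not above 200. This shows incoherence only; it does not change ORR or CBr.

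**Size per misclassified patient.**

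- Myeloma ORR: 1/8 = 12.5 points; 1/15 = 6.7 points.
- Pooled ORR: 1/38 = 2.6, 1/44 = 2.3, 1/51 = 2.0 points.
- Illustration with assumed counts: 2/8 has an exact 95% interval of 3.2–65.1%, and 3/8 has 8.5–75.5%.

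**The case against.** **It may be a reading error.** Everything rests on one character in machine-read text. The same list prints a plasma-cell limit of at most 5% for stringent CR and below 5% for plain CR, so its comparison signs are not beyond doubt. This stands, and it is why the source check comes first.

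**A governing standard is named.** Section 12.1 says responses follow the IMWG criteria, and 16.1.2 makes them subject to central committee review. Experienced reviewers would probably not credit a fall from 1,000 to 900. This lowers the likelihood of harm, but 12.1.1 sets out the operative definitions and 16.1.2 supplies no alternative rule. A reviewer who applies the intended threshold departs from the written protocol, and one who follows the protocol misclassifies.

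**The low-baseline example is out of scope.** Section 12.1.1 addresses patients with measurable M-protein, and a baseline of 150 is below the urine entry threshold. In part this stands: the text does not say whether the urine condition applies to a patient measurable by serum only. But such patients can enter on serum disease, nothing waives the condition, and 12.1.2 anticipates low-level urinary protein. The ORR loss also occurs at a baseline of 1,000 (150, then 120 and no lower), so the conclusion does not depend on this example.

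**It is minor.** The endpoints are secondary and descriptive, the per-patient shifts are simply 1/n, and non-monotonicity is confined to baselines above 200 and up to 2,000. All true. Outside that range the limb still misclassifies, being either unreachable or met by any fall.

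**Conclusion.** The point holds as the text is printed. The absolute urine limb contradicts the direction of the VGPR, PD and entry thresholds, and no other section corrects it. Applied literally, it misclassifies serum responders in both directions and can move the first response by one or two cycles in the sequences shown.

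Each misclassified patient moves the myeloma ORR by 12.5 points (n=8) or 6.7 points (n=15), and the pooled ORR by 2.0 to 2.6 points. The number of such patients cannot be derived, because no distribution of baseline urine M-protein is given.

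This rests on the sign being the same in the source PDF and on the printed rule being the one applied. It should be fixed, with medium confidence because of the single character. The primary objective and the design are unaffected.

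**What to change.** 1. Confirm the sign in the source PDF.
2. If it is as printed, change the absolute limb of the PR definition in 12.1.1 to a reduction to below 200 mg/24 h, leaving the limb of more than 90% unchanged.
3. Establish which rule the response reviewers applied.
4. Only if it was the printed rule, re-check the per-cycle calls of myeloma patients with a serum fall of 50% or more and any urine M-protein at baseline, including baselines below 200. Best response alone is not enough, because TTR and DOR use the first qualifying assessment.

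Optionally, state how the urine condition applies to patients measurable by serum only or urine only; that is a separate clarification.

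The cost is a one-character correction after a source check. Any re-check covers a subset of roughly 8 to 15 myeloma patients. Section 4.1 counts phase Ib patients treated at the MTD toward phase IIa accrual, so that range probably already includes them.

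### Myeloma PR, apart from the FLC route, needs a serum M-protein fall, so a patient who enters on urine alone with no serum M-protein cannot be PR, and urine falls of 50% or more short of VGPR have no category

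*Combined protocol and SAP*

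**What the plan says.** Section 6.1, criterion 3, is headed "Measurable disease for phase IIa portion only". For myeloma it reads "Patient must have measurable disease and therefore must have at least one of the following": serum M-protein of at least 0.5 g/dL, urine M-protein of at least 200 mg/24 h, or involved FLC of at least 10 mg/dL with an abnormal ratio. Any one is enough.

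Section 12.1.1 then defines the response categories:

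- **PR:** "50% or greater reduction of serum M-protein and reduction in 24-hour urinary M-protein", where the urine part is a fall of more than 90% or an absolute limb printed as to >200 mg/24 h. The one substitute is "If the serum and urine M-protein are not measurable, a decrease of 50% in the difference between involved and uninvolved FLC levels is required".
- **VGPR:** either M-protein seen on immunofixation but not on electrophoresis, or a fall of at least 90% "in the M-protein concentration component plus a urine M-component" below 100 mg/24 h.
- **MR:** "Minimal Response (MR) = A reduction of" more than 25% but less than 50% in M-protein concentration, with no compartment named.
- **SD:** a change of less than 25% in either direction, again with no compartment named.
- **PD:** a rise in urine alone can be enough.

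Section 4.1 counts CR, VGPR and PR towards ORR, and states that "CBr is defined as CR, VGPR, PR or MR (minimal response) in myeloma patients". Time to response ends, and duration of response starts, at the first CR, VGPR or PR.

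**The concern.** The entry rule and the PR rule do not match. Entry asks for one measurable compartment, whereas the M-protein route to PR asks for a response in two. Nothing in 12.1.1 limits the PR test to the compartment that was measurable at entry, and the FLC substitute is closed to anyone whose urine is measurable. A patient with urine disease and no serum M-protein has nothing in serum to halve, so the serum condition cannot be met however far the urine falls. The same patient can still be scored PD on urine.

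At stake is how the myeloma cohort's activity is reported. A patient in the gap is lost from ORR. If that patient later reaches VGPR, response is dated from the VGPR, which lengthens time to response and shortens duration of response. Section 4.1 says the phase IIa efficacy data are meant to inform a possible subtype-specific phase II study.

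**Working it through.** The plan states no figure that depends on these definitions, so there is nothing to reproduce. The check applies the 12.1.1 thresholds literally.

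**Assumptions for the table.** Serum M-protein is zero, urine M-protein is still visible on electrophoresis (so the first VGPR limb is not met), and the unnamed M-protein in MR, SD and the second VGPR limb is read to include urine. Fall = (baseline − follow-up) / baseline.

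| Baseline urine (mg/24 h) | Follow-up | Fall | Category as written |
|---|---|---|---|
| 3,000 | 2,100 | 900/3,000 = 30% | MR |
| 3,000 | 1,200 | 1,800/3,000 = 60% | none |
| 3,000 | 240 | 2,760/3,000 = 92% | none (urine not below 100) |
| 3,000 | 90 | 2,910/3,000 = 97% | VGPR |
| 1,000 | 600 | 400/1,000 = 40% | MR |
| 1,000 | 150 | 850/1,000 = 85% | none |
| 1,000 | 80 | 920/1,000 = 92% | VGPR |
| 500 | 75 | 425/500 = 85% | none |
| 500 | 50 | 450/500 = 90% | VGPR |

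PR is not reached in any row. The gap runs from a 50% fall up to the VGPR threshold. It is not SD, because SD stops at 25%.

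**Limits of the finding, on the same text.**

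- FLC-only patient, 60% fall in the FLC difference: PR, with no serum M-protein fall.
- Patient who enters on urine but has a detectable serum value below the entry threshold: serum 0.4 to 0.2 g/dL is 50%, and urine 2,000 to 150 is 1,850/2,000 = 92.5%. Both conditions are met, so this is PR.

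**Would scoring urine-only patients on the urine condition alone be enough?** No, because of the absolute limb.

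- As printed (to >200): 3,000 to 2,100, a 30% fall, ends above 200 and would be PR. 1,000 to 150, an 85% fall, is neither above 90% nor above 200, so it would not.
- With the sign reversed: 1,000 to 150 qualifies, but 1,000 to 300 (70%) meets neither limb and is still unclassified.

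**Size per patient.** Section 14 plans 8 myeloma patients; Sections 4.1 and 9.3 give 15. One patient is 1/8 = 12.5 points or 1/15 = 6.7 points of myeloma ORR. Against the roughly 44 patients in Section 14, it is 1/44 = 2.3 points of pooled ORR.

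**Number of patients.** The documents give no urine-only share. If it were 10–20% (assumption), entrants would number 0.10 × 8 = 0.8 to 0.20 × 15 = 3.0. Only those whose response falls in the gap are affected. If that were 30% of them (assumption), the count would be 0.3 × 0.8 = 0.24 to 0.3 × 3.0 = 0.9.

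**The case against.** **The protocol invokes the IMWG criteria, and a committee reviews responses.** Section 12.1 names the IMWG criteria and Section 16.1.2 makes responses subject to central review. In practice a reviewer may score urine-only disease sensibly, so mis-scoring is not certain. But 12.1.1 writes out its own definitions, and no rule in the documents covers urine-only disease or says which text prevails. The committee would have to supply the rule itself.

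**The inversion depends on a mixed reading.** A reader might infer that larger falls score worse than smaller ones. That takes MR as covering urine while PR is held to serum plus urine. If MR and the second VGPR limb are confined to serum, a 30% urine fall is not MR either and the inversion disappears. If PR is read as loosely as MR, the gap narrows. This objection stands in part: the inversion is conditional, and a 60% fall lands in no category rather than in a named worse one. Still, with PR confined to its own wording, no reading of the other categories makes it reachable for a patient with no serum M-protein.

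**Clinical benefit rate is partly protected.** Section 4.1 scores ORR on best response at any assessment, and myeloma is assessed every cycle. If clinical benefit is scored the same way, a patient who passed through MR keeps that credit. Only a patient who moves past MR between two assessments loses it. This stands.

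**The endpoints are secondary and imprecise.** The primary objective in Sections 1 and 2 is MTD and safety, and disease-specific analyses are exploratory. With 8 patients, 2/8 is 25.0% (exact 95% CI 3.2–65.1) and 3/8 is 37.5% (8.5–75.5). This limits the importance but does not make the rule usable.

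**Conclusion.** The point holds in a limited form. For a phase IIa myeloma patient with measurable urine and no serum M-protein, PR cannot be met as written, and a urine fall of 50% or more short of VGPR has no category. Below that, a fall of more than 25% but less than 50% is MR only if the unnamed M-protein includes urine, which is reasonable but unstated.

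The effect is confined to secondary endpoints: myeloma and pooled ORR, time to response, duration of response, and clinical benefit rate only where no earlier assessment scored MR. Each affected patient is worth 12.5 points of myeloma ORR at n=8 or 6.7 at n=15. The total cannot be computed from the documents; one or two patients at most is a judgement resting on the assumed shares above.

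Three stronger readings are not supported. A reader might infer that PR always requires a serum fall, but the FLC route in the same definition contradicts this. A reader might infer that anyone who enters on urine can never be PR, but a detectable serum value below the entry threshold is enough to meet the wording. And a reader might infer a known bias of one to three patients, but that figure would count every assumed urine-only entrant, not those whose response lands in the gap.

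**What to change.** Make one edit to 12.1.1 with four parts, which need to go in together:

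1. State that PR is judged on the compartment or compartments measurable at entry: the serum condition for serum-only patients, the urine condition for urine-only patients, both when both are measurable.
2. Resolve the direction of the absolute urine limb now printed as to >200 mg/24 h. Part 1 fails without this.
3. Name the compartment to which MR, SD and VGPR apply.
4. Assign a category to urine falls from 50% up to the urine PR threshold, so that the categories are ordered and leave no fall unclassified.

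The cost is a few sentences and an amendment. No tests are added: Section 12.1 already has serum and urine electrophoresis at the end of every cycle, so patients already assessed can be rescored from existing results.
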